The primary objective is to assess the efficacy of fractionated carbon dioxide laser in improving surgical scars. Objective assessment of the scars will involve the Vectra microtopographic imaging system to measure changes in the length of the scar. The Patient and Observer Scar Assessment Scale (POSAS) is a validated survey that will be utilized for subjective assessments of the vascularity, pigmentation, thickness, pliability, surface area, relief, pain, and pruritus.

The secondary objective will be to evaluate the tolerability of the laser, by assessing the severity and duration of known side effects of laser therapy such as erythema, edema, burning sensation, post-inflammatory pigment changes, infection, scarring, xerosis, pruritus, bronzing, and any other adverse events that arise following treatment. Patients will be given a 30-diary after each treatment to document this information.

Selection and Withdrawal of Study Subjects

Study Population

The study population will consist of 50 adult patients 18 years of age or older with surgical scars located on the head and neck.

Minors are not included due to the Mohs patient population being adults only who have undergone surgical excisions of skin cancers on the head or neck. Although participants are not

required to be patients in the Mohs clinic, scars and healing may be significantly different in children, making the data less reliable and difficult to interpret.

Inclusion and Exclusion Criteria

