For the inclusion criteria, adult patients of all Fitzpatrick phototypes who have surgical scars of the head and neck will be screened for this study. There is no data to suggest that there is a difference in the appearance of older (more than 1 year old from the initial injury) and newer scars (at least 8 weeks after surgery) post-therapy. Most scars are fully mature at exactly 1 year from the date of the initial injury, so in the "older scar" cohort one may presume (in the absence of any confirmed findings in the medical literature) that any changes to these scars post-therapy will be an effect from the laser. The minimum age of the scar will be eight weeks from the initial surgery, as the scar has healed enough to determine if additional fine tuning may be helpful. In addition, standard practice is to allow a scar to heal for 8 weeks before laser treatment. Therefore subjects may be enrolled in the younger scar group if the scar is 8 weeks – 51 weeks from occurrence, and enrolled in the older scar group if the scar is 52 weeks or older from time of occurrence. We will aim to recruit 20 patients with old scars (10 of which will be in the high energy treatment group, and 10 of which will be in the low energy treatment group). In terms of statistical analysis, we will review whether there is a difference between the post-treatment measurements and appearance of older scars and newer scars. Patients must be able to understand the informed consent, willing to come to the office for treatments and capable of following post-treatment instructions.

In terms of exclusion criteria, patients who have had prior laser treatments to the face and neck, have a history of keloid formation, scars resulting from non-surgical etiologies (i.e. minor trauma), isotretinoin use in the last 6 months prior to study enrollment, and allergy to topical lidocaine will not be eligible for the study.

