A screening visit will occur whereby patients deemed appropriate for the study will have the segment of the scar with the most deformity defined for objective evaluation at each session. Baseline photographs of this area will be obtained and demographic data about the surgery that created the scar, associated wound healing complications, age of the scar, and the Fitzpatrick skin phototype will be collected. Randomization will occur at this visit and patients will receive their first treatment at this visit. Prior to treatment application, subjects will cleanse their face with a gentle cleanser, such as Cetaphil, provided in the office in order to remove all lotion, creams, make up, and sunscreen. An optional topical or local anesthetic medication will be offered to the subject and if desired by the subject will be applied to the treatment area approximately 20 minutes prior to the procedure. If the scar is deeper, an injection of numbing medicine (lidocaine with epinephrine) may be used as well. Once this time passes and the numbing medicine is working, the subject will be escorted to the procedure room. The treatment areas will be wiped clean of the numbing cream prior to the procedure. Just prior to the procedure, the subject's eyes will be covered with eye shields to protect their eyes. The treatment time may vary, but generally takes 10 minutes or less. During this time, subjects will hear the laser, which sounds like a bee buzzing, and will feel some warmth. Most patients report minimal discomfort during the procedure. There may be pinpoint bleeding, bruising, and crusting depending upon the area and extent of the treatment. After the treatment, patients will be provided with a 30-day diary to daily record treatment-related reactions: redness, swelling, pain, itching or color changes following treatment. If the subject has a history of recurrent fever blisters/cold sores on the lips or face, the subject will be offered a three day prescription for an antiviral medication that the subject can fill at the subject's pharmacy to prevent a recurrence since laser treatments may increase the chance of recurrent episodes. The subject would take one pill every twelve hours the day prior to treatment, on the treatment day, and the first day post-treatment. The subject or their insurance plan must cover the cost of the medication. This may delay the treatment to a later date within 30 days of the screening visit. If antibiotic/antiviral medications are needed, you and/or your insurance company will be responsible for covering this cost.

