As soon as the PI becomes aware of an AE that meets the criteria for an SAE, the SAE should be documented to the extent that information is available. A report must be submitted by the study site to the SLU IRB, within 24 hours. Forms for reporting SAEs will be provided to the study site. SAEs will be recorded from the time of informed consent, through the end of the study. If in the opinion of the Investigator, an SAE occurring outside the specified time window (i.e., following subject completion or withdrawal from the study), is deemed to be device related, then the event should be reported with 24 hours as outlined above. The Investigator should institute any clinically necessary supplementary investigation of SAE information.

Death

In the case of subject death, any post-mortem findings/reports will be requested and a report (even if a preliminary diagnosis/cause of death is available) will be submitted to the SLU IRB within 24 hours of learning about the death.

Reporting of Pregnancy

In the case of subject pregnancy, the subjects will be discontinued from the study and will be followed leading up to delivery.

Data Analysis and Statistical Considerations

At the completion of the study, the data obtained will be reviewed and analyzed with the aid of the Saint Louis University Center for Health Outcomes Research. A chi-square test along with the Wilcoxon signed rank test will be performed to assess significant difference between clinical improvement scores between study visits. There is no data to suggest that there is a difference in the appearance of older (more than 1 year old from the initial injury) and newer scars post-therapy. We will aim to recruit 20 patients with old scars (10 of which will be in the high energy treatment group, and 10 of which will be in the low energy treatment group). In terms of statistical analysis, we will review whether there is a difference between the post-treatment measurements and appearance of older scars and newer scars.

Quality Control and Quality Assurance

Quality control and assurance for this study will be performed by an internal review every 3 months to ensure that the data collected is in accordance with the goals of this study and to address any issues with data collection or performance of any study procedures.

Direct Access, Data Handling and Record Keeping

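### The older-versus-newer scar comparison is described on post-treatment values with no baseline term, so a gap present before treatment or due to natural maturation could be read as a difference in response

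*Combined protocol and SAP*

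**What the plan says.** The comparison appears twice in the same words, under Inclusion and Exclusion Criteria and under Data Analysis and Statistical Considerations: "we will review whether there is a difference between the post-treatment measurements and appearance of older scars and newer scars". Neither place mentions a baseline value, a change score, a visit or a test for it.

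The only tests named are in the analysis section: "A chi-square test along with the Wilcoxon signed rank test will be performed to assess significant difference between clinical improvement scores between study visits". That sentence concerns differences between visits and is not linked to scar age.

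Scar age is a subject characteristic. Newer scars are 8 to 51 weeks old, and a subject is "enrolled in the older scar group if the scar is 52 weeks or older from time of occurrence". The eligibility section also states: "Most scars are fully mature at exactly 1 year from the date of the initial injury". It presumes, for the older group, that later change will be an effect of the laser. It adds that no data suggest a difference in post-therapy appearance between older and newer scars.

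On numbers: "The study population will consist of 50 adult patients 18 years of age or older" (Study Population) and "We will aim to recruit 20 patients with old scars", 10 in each energy arm.

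Baseline data exist. Under Study Procedures, "Baseline photographs of this area will be obtained" and scar age is recorded. Study Visit #1 adds a patient questionnaire and a physician evaluation of the scar.

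**The concern.** Randomisation balances the energy arms. It does not balance older against newer scars. A difference between the scar-age groups after treatment has at least three possible sources:

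- the scars looked different before treatment;
- newer scars matured over the months of follow-up regardless of laser;
- the laser worked differently.

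The protocol's reasoning about maturity at one year makes the first two plausible. The contrast as written cannot separate the three. If it were followed literally, the trial could report that laser works better in one scar-age group when the groups merely started apart, or it could miss a real difference hidden by an opposite starting gap. No other sentence in the plan repairs this. The signed rank test is paired, so it cannot compare two independent groups.

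**Working it through.** The plan states no alpha, SD, effect size or power, so there is no figure of its own to reproduce. What follows is illustration under stated assumptions.

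**Inputs from the documents.** Total 50, older scars 20 (10 per arm). Newer scars by subtraction: 50 − 20 = 30, if both targets are met.

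**Assumed inputs.** Two-sided 5% t-test; SD 1 at each time; baseline gap D of 0.5 or 0.8 SD; baseline-to-follow-up correlation r of 0.5 to 0.7; 15 newer scars per arm.

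**1. Post-treatment comparison, no baseline term.** The standard error is √(1/20 + 1/30) = 0.289 SD. Two cases bracket what may happen to the gap when the laser has no differential effect:

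- *The gap shrinks.* Both groups follow one regression line on baseline, so the gap left at follow-up is r × D.
- *The gap persists.* Both groups have the same mean change, so the gap left is D.

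| Baseline gap D | Case | Gap at follow-up | Chance of a false difference |
|---|---|---|---|
| 0.5 SD | shrinks, r = 0.5 | 0.25 SD | 13.6% |
| 0.5 SD | shrinks, r = 0.7 | 0.35 SD | 22.1% |
| 0.5 SD | persists | 0.50 SD | about 40% |
| 0.8 SD | shrinks, r = 0.5 | 0.40 SD | 27.4% |
| 0.8 SD | shrinks, r = 0.7 | 0.56 SD | 47.7% |
| 0.8 SD | persists | 0.80 SD | about 78% |

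The percentages come from the noncentral t distribution with 48 degrees of freedom and noncentrality equal to the follow-up gap divided by 0.289.

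**2. Does adding baseline as a covariate cure the older-versus-newer main effect?** Only in the first case. If the gap persists, the adjusted scar-age term is off by D − r × D = (1 − r) × D:

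- D = 0.5: 0.25 SD at r = 0.5 and 0.15 SD at r = 0.7. Simulated false-positive rate about 16% and 11%.
- D = 0.8: 0.40 SD and 0.24 SD. Simulated rate about 30% and 18%.

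A change score holds about 5% if the gap persists. Neither method removes maturation that occurs only in newer scars.

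**3. Arm-by-scar-age interaction with baseline in the model.** Maturation common to both arms cancels in the high-minus-low difference within each scar-age group. In simulation the false-positive rate stayed near 5% for D = 0.5 and 0.8 and r = 0.5 and 0.7, in both cases.

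**4. Power of that interaction.** The standard error is √(1 − r²) × √(1/10 + 1/10 + 1/15 + 1/15) = √(1 − r²) × 0.577. That is 0.50 SD at r = 0.5 and 0.41 SD at r = 0.7. For a true interaction of 0.5 SD the noncentrality is 1.00 to 1.21, and power is about 17% to 22%.

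**The case against.** The plan does not say that baseline will be ignored. A reader might infer a decision to compare post-treatment values alone, but the text is only silent. Nearby wording is about change: the named tests act on improvement between visits, the primary objective is to "measure changes in the length of the scar", and the scar-age paragraph itself speaks of changes after therapy. This stands as a limit on the criticism. It does not settle the matter, because none of that wording is applied to older versus newer scars, and the choice is left open until the data are seen.

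A reader might also infer that the groups do differ at baseline. The documents report no such gap and no direction, and every subject is assessed on the most deformed segment of the scar. A gap is plausible from the maturity statement but is not established.

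Nor do the documents say that the 20 older scars are recruited for this comparison. The recruitment target stands beside it, and the stated reasoning is that change in a mature scar can be presumed to come from the laser.

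Finally, this is a loosely worded review and not a stated objective, and the replacement analysis has little power. Both points stand. They bear on how much weight the result can carry. They do not make the planned contrast interpretable.

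**Conclusion.** The concern holds in a limited form. The sole description of the scar-age comparison lacks a baseline term, the groups are not randomised, and a post-treatment gap between them could not be attributed to laser response.

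The size is conditional. An assumed 0.5 SD baseline gap gives a false difference 14% to 22% of the time if it shrinks and about 40% if it persists. At 0.8 SD the figures are 27% to 48% and about 78%. All rest on 20 versus 30 subjects, a two-sided 5% test and assumed gaps and correlations.

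It is tempting to conclude that adjusting for baseline removes the problem. For the older-versus-newer main effect it does not, unless the gap shrinks exactly as r × D, and natural maturation remains in any case. Only the interaction with randomised arm avoids both, provided the arms are comparable within each scar-age group. It answers whether the high-minus-low difference varies with scar age. It does not show how much laser as such helps each group, because no arm is untreated.

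This is worth correcting because the correction is nearly free, but it concerns a secondary, exploratory question.

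**What to change.** Replace the sentence in both sections with a specified analysis:

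- **Outcome and visit:** each POSAS score (patient and observer) and the Vectra measurement, at Visit 3, before any optional treatment.
- **Model:** Visit 3 value on baseline value, arm, scar-age group and arm-by-scar-age interaction.
- **Report:** the high-minus-low difference with 95% CI within each scar-age group, and the interaction with its 95% CI. As a sensitivity analysis, use recorded scar age in place of the two groups.
- **Interpretation:** base the scar-age conclusion on the interaction. State that the scar-age main effect will not be read as laser response.
- **Status:** exploratory, with a statement that power is low with about 10 older scars per arm.

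The cost is wording only. Baseline photographs and ratings, scar age, arm and Visit 3 assessments are already collected, and no extra subjects or visits are needed.
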